7.17.3 Screen Failures

A Screen Failure is defined as any subject that has given consent to participate in the study (i.e. signed an Informed Consent Form) and subsequently was not enrolled for IUS insertion.

7.17.4 Missed Visits/Contacts and Lost to Follow Up

All reasonable efforts should be made to ensure that subjects in screening and enrolled subjects return to the investigational site for all study visits. Once a subject is designated as lost to follow-up, no additional information is to be obtained on any outcomes and no further study-related activities are to be conducted, even if the subject later resumes contact.

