7.4 Pregnancy Assessment and Reporting

High sensitivity urine pregnancy tests are performed at each study visit. For any positive pregnancy test on IUS treatment through Visit 8/Early Discontinuation:

- Immediately obtain a serum quantitative hCG
- Within 3 calendar days conduct a transvaginal ultrasound for pregnancy confirmation, pregnancy location and date of conception
 - If the pregnancy is too early for ultrasound verification have the subject return in approximately 1-2 weeks for an unscheduled visit and repeat ultrasound examination
- Complete a Pregnancy Narrative (See Study Reference Manual)

If the subject reports a positive pregnancy test on her own (performed at home) she should be seen as soon as possible for a high-sensitivity urine pregnancy test to be performed at the clinic and if the test is positive perform the required procedures above.

For pregnancies occurring before IUS discontinuation, ultrasonography will also be used to verify presence of the IUS in the uterus.

All confirmed pregnancies occurring during study treatment will be followed to completion.

Pregnancy outcomes, including normal births, septic abortions, ectopic pregnancies, birth defects, and premature deliveries, whenever this information is available, will be obtained. Pregnancy reporting should include a Pregnancy Report Form Case Report Form (CRF) and Pregnancy Outcome CRF.

Pregnancy management is outlined in Appendix F.

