7.16 Post-Study Treatment Reporting Requirements

For all enrolled subjects, all AEs and SAEs, regardless of cause or relationship that occur from IUS discontinuation through the Safety Follow-up require reporting to the Sponsor. In addition, if the Investigator learns of any SAE at any time after a subject has discontinued study drug, and such event seems reasonably related to study drug, the Investigator should promptly notify the Sponsor.

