7.17.2 Withdrawal from the Study

The following criteria will be used to determine when a subject should be withdrawn from the study:

- A subject may withdraw consent for further participation in the study at any time without giving a reason

- A subject may choose to stop participation in the study for any reason. If the subject has not withdrawn consent and has an IUS in place they should be brought in for IUS removal and have appropriate safety follow-up procedures.
- A subject may also be discontinued from the study at the request of the Investigator or the Sponsor. If the subject has an IUS in place they should be brought in for removal and have appropriate safety follow-up procedures.
- Sponsor decision to terminate the study or discontinue the investigative site's participation

Reasons for subject withdrawal from the study should be documented in the subject's file and entered into the CRF.

Subjects that are designated as withdrawn from the study, lost to follow-up or who withdraw consent may not re-enter the study and no further data collection will occur.

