7.17.4.2 After Enrollment

Any subject who misses a scheduled visit should have further contact attempts by the study staff as follows:

- At least three documented attempts to contact the subject by phone, e-mail or similar mode of communication
- If the subject cannot be contacted, or is contacted and still fails to come in for a scheduled visit, a certified letter must be sent to the subject indicating the importance of follow-up and instructed to contact the site immediately
- If subject contact for either a missed Visit 6 or Visit 7 is unsuccessful then future attempts should be made at the time of the next expected study visit
 - At least three documented attempts to contact the subject by phone, e-mail or similar mode of communication should be completed
 - If the subject cannot be contacted or is successfully contacted but still fails to be seen for a scheduled study visit, a certified letter must be sent to the subject indicating the importance of follow-up and should be instructed to contact the site immediately. The letter should indicate that failure to reply within 30 days of the letter date will result in study discontinuation and no future study-related activities will be provided. Certified letters do not need to be sent for subsequent missed study visits if a previous delivery attempt was unsuccessful (letter returned or accepted with no subsequent response).

A subject should be considered lost to follow-up when:

- A subject in the Treatment Phase does not report for V8
- The safety follow-up contact (if applicable) is missed and three documented contacts and a certified letter do not result in subject contact within 14 days of the end of the expected contact window

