6. ANALYSIS POPULATIONS

The Safety population will include all subjects enrolled who underwent an IUS insertion attempt, regardless of outcome.

The following subject populations will be used for efficacy analyses:

- Modified-Intent-To-Treat (MITT): All subjects with qualifying baseline data at study entry for whom the IUS is successfully inserted and for whom there is at least one assessment of MBL during the Treatment Phase Cycle 3 or Cycle 6. All MBL values reported for both validated and unvalidated used feminine hygiene products will be included. This is the main population for the efficacy analyses.
- Supportive MITT: A supportive subset of the MITT population with baseline and post-baseline MBL data reported collected from only validated feminine hygiene products. This population is to demonstrate the robustness of the efficacy analyses.
- Per Protocol (PP): A subset of the MITT population that excludes subjects with major protocol deviations that are determined to have impact on the data of MBL assessment.

- Intent-to-Treat (ITT): All subjects with qualifying baseline data at study entry for whom the IUS is successfully inserted. This population is for evaluation of the sensitivity of results obtained from the MITT-based assessments. The baseline MBL will be carried forward (BOCF) for subjects who provide no Treatment Cycle 3 and no Treatment Cycle 6 data.
- Intent-to-Treat (ITT) Excluding Subjects LTFU and Subjects Who Withdraw Consent (WC) Without Study IUS Removal: All subjects with qualifying baseline data at study entry for whom the IUS is successfully inserted, excluding subjects who were LTFU or withdrew consent without study IUS removal and had no MBL assessment after baseline at Treatment Cycle 3 and Cycle 6. The baseline MBL will be carried forward (BOCF) for subjects who provide no Treatment Cycle 3 and no Treatment Cycle 6 data except for those subjects who were LTFU or withdrew consent without study IUS removal. This population is for evaluation of the sensitivity of results obtained from the MITT-based assessments.

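### Protocol 7.17.4 and 7.17.2 bar recording any outcome after loss to follow-up, which contradicts the SAE and pregnancy rules and leaves late-learned non-serious device events uncollected

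*Protocol*

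**What the plan says.** Three protocol passages close the record at LTFU.

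- 7.17.4: after designation, "no additional information is to be obtained on any outcomes and no further study-related activities are to be conducted", and this holds even if contact resumes.
- 7.17.2: women who are withdrawn, lost to follow-up or withdraw consent "may not re-enter the study and no further data collection will occur".
- 7.14: follow-up of IUS-related and procedure-related events runs to resolution or stabilization, but stops if the woman is lost to follow-up.

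The Treatment Phase trigger in 7.17.4.2 is short: "A subject in the Treatment Phase does not report for V8". The Visit 8 window closes on Day 189 (6.10).

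Other passages point the opposite way.

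- 7.8 requires reporting of all SAEs that occur from screening through Visit 8 or early discontinuation and any post-treatment safety contact.
- 7.16 asks the site to notify the sponsor "if the Investigator learns of any SAE at any time after a subject has discontinued study drug", where the event seems related.
- 7.4 says: "All confirmed pregnancies occurring during study treatment will be followed to completion". Section 7.1.3 says the same of pregnancies during IUS use.

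None of these mentions LTFU.

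On the analysis side, SAP 11.6 censors women without an event at last contact. The SAP definition of a treatment-emergent event ends at last known IUS use or the safety contact, whichever is later. SAP 6 defines an ITT sensitivity set "excluding subjects who were LTFU or withdrew consent without study IUS removal and had no MBL assessment after baseline" at Cycle 3 and Cycle 6.

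**The concern.** LTFU and withdrawal of consent are separate categories in 7.17.2, so a lost woman has not asked for data collection to stop. The documents also accept that her device may still be in place: Protocol 7.11 lists loss before IUS removal, and SAP 6 builds a population around it. Appendix G notes that a perforation may be found only later and that an expulsion can go unnoticed. SAP 10.1 adds that, in the pandemic, lost women may simply have been unable or unwilling to attend. Some may therefore call again, which is the case that 7.17.4 closes off.

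Two things are at stake. First, a site told of an SAE or pregnancy after designation holds opposite instructions. Second, non-serious device outcomes that feed the expulsion, continuation and safety-removal rates are lost even when the woman volunteers them.

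**Working it through.** **The plan's own figure.** The lower bound is p − 1.96 × √(p(1−p)/n). With p = 0.80 and n = 85: 0.80 − 1.96 × 0.0434 = 71.5%, as in Protocol 9.1. With n = 80: 71.2%, as in SAP 4. The finding does not depend on these figures, but the same formula is used in the last step.

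**Provisions side by side, for information first learned after designation.** The bar is 7.14, 7.17.2 and 7.17.4 throughout.

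| Event | Competing provision | Result |
|---|---|---|
| SAE that occurred through Visit 8 | 7.8, keyed to when the event occurred | Contradiction |
| Related SAE, device no longer in use | 7.16 | Contradiction |
| Related SAE after the Visit 8 window, device still in place | 7.16 is worded for women who have discontinued study drug; 7.8 has ended | Not clearly covered |
| Pregnancy during IUS use | 7.1.3, 7.4 | Contradiction |
| Non-serious expulsion, removal elsewhere, non-serious device AE on study | No late-reporting provision; 7.6 and 7.10 set AE recording by onset date only | Not collected |

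**Kaplan-Meier rates (illustration).** Inputs: 100 women inserted; first-year expulsion of 3.9% (Protocol 7.1.5, probably high for six months) in women who are followed; L women lost with unseen events; true expulsion rate r among them. L and r are assumptions. The documents give only all-cause dropout, 15–20% in SAP 4, so L = 15–20 would mean that every dropout is LTFU.

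Overall rate = [(100 − L) × 3.9% + L × r] / 100

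| L | r = 3.9% | r = 10% | r = 20% |
|---|---|---|---|
| 5 | 3.9% | 4.2% | 4.7% |
| 15 | 3.9% | 4.8% | 6.3% |
| 20 | 3.9% | 5.1% | 7.1% |

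For example, L = 15 and r = 20%: (85 × 3.9% + 15 × 20%) / 100 = 6.3%. With r = 3.9%, loss is unrelated to expulsion and there is no bias. The chance of at least one expulsion among the lost, 1 − (1 − 0.039)^L, is 18% for L = 5, 33% for L = 10 and 55% for L = 20. For perforation at 0.1% (7.1.7) it is 0.5% to 2.0% over the same range.

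SAP 11.6 also censors expulsions that the site has not confirmed. Since 7.17.4 bars further study activity, an expulsion reported by telephone after designation would probably be censored even if it were written down.

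**Efficacy populations, for a woman with no Cycle 3 and no Cycle 6 MBL.**

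- MITT with LOCF (principal analysis): she is not in it, whatever is learned later.
- Full ITT: her baseline is carried forward, so she fails the 50% criterion and is already a failure.
- ITT excluding LTFU women without IUS removal: she is left out, whereas known removal elsewhere would make her a carried-forward failure. This reads the removal qualifier as applying to LTFU as well as to withdrawal of consent.

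With assumed counts in the third analysis: 72/90 = 80.0% (lower bound 71.7%). One such woman restored: 72/91 = 79.1% (70.8%). Two: 72/92 = 78.3% (69.8%).

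**The case against.** The strongest reply is that the protocol does not lose these events wholesale. Section 7.8 turns on when an SAE occurred, 7.16 on what the investigator learns, and 7.4 on whether a pregnancy was on treatment, so a careful site could read 7.17.4 as barring only active pursuit. Data recorded before designation are kept. This stands in part. A reader might infer that every perforation, expulsion, pregnancy and outside removal is discarded, and the documents do not support that. For SAEs and pregnancies the defect is a contradiction, not a certain loss. It remains a contradiction, because 7.17.4 speaks of any outcomes and makes no exception. The general AE rules in 7.6 and 7.10 soften the last row of the provisions table, but they do not address information that arrives after designation.

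A reader might also picture a call shortly after Day 189 being refused. That is uncertain: 7.17.4.2 provides contact attempts and a certified letter after any missed visit, so the call may precede designation.

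Nor do the documents support a general inflation of efficacy. A woman whose device came out in month 4 has normally completed the Cycle 3 collection (Days 57–84) and stays in MITT by LOCF.

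Finally, women who complete Visit 8 may keep the IUS with no further scheduled follow-up, so later events in device carriers are not peculiar to LTFU. That is fair. The gap concerns events during the study period that come to light after designation.

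**Conclusion.** The passages contradict each other on SAEs and pregnancies, and nothing clearly provides for late-learned non-serious expulsions, outside removals and device events. The effect falls on safety capture and on the Kaplan-Meier expulsion, continuation and safety-removal rates. It is zero if loss is unrelated to the event. If it is related, the expulsion rate rises from 3.9% to between 4.2% and 7.1% over the assumed ranges (L = 5 to 20, r = 10% to 20%). Expected perforations among the lost are close to none.

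The principal efficacy result and the full ITT analysis do not change for women without post-baseline MBL. The one exposed sensitivity analysis moves by about one percentage point per misclassified woman. That requires no MBL at either cycle, removal elsewhere and renewed contact after designation, so the number of such women should be well below the number lost, and the documents give neither. The point justifies a wording change, but it does not call the primary conclusion into question.

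**What to change.** - **Protocol.** Reconcile 7.14, 7.17.2 and 7.17.4 with 7.1.3, 7.4, 7.8 and 7.16 by limiting the bar to scheduled visits and to MBL and diary collection. State that, unless consent is withdrawn, the site records what it learns before database lock on IUS status (in place, expelled or removed, with date and reason), SAEs, IUS-related AEs and pregnancies.
- **SAP 6.** Use this information when classifying women as LTFU without IUS removal, and make clear that the removal qualifier covers LTFU.
- **SAP 11.6 and the treatment-emergent definition.** Say how late-learned dates enter the Kaplan-Meier analyses and the event window, including what counts as confirmation of an expulsion reported after designation.

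The cost is a few sentences in each document and no added visits, since the site records only what reaches it. The consent form is not among the documents, so check that it allows use of information from another provider. The downside is a few late safety records and possibly slightly less favourable expulsion, continuation or sensitivity-analysis rates.

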7.17.4.1 During Screening

Any subject who misses a scheduled visit should have further contact attempts by the study staff as follows:

- At least three documented attempts to contact the subject by phone, e-mail or similar mode of communication

- If the subject cannot be contacted, or is contacted and still fails to come in for a scheduled visit, a certified letter must be sent to the subject indicating that she will be considered a screen failure (lost to follow-up) and cannot continue in the study

7.17.4.2 After Enrollment

Any subject who misses a scheduled visit should have further contact attempts by the study staff as follows:

- At least three documented attempts to contact the subject by phone, e-mail or similar mode of communication
- If the subject cannot be contacted, or is contacted and still fails to come in for a scheduled visit, a certified letter must be sent to the subject indicating the importance of follow-up and instructed to contact the site immediately
- If subject contact for either a missed Visit 6 or Visit 7 is unsuccessful then future attempts should be made at the time of the next expected study visit
 - At least three documented attempts to contact the subject by phone, e-mail or similar mode of communication should be completed
 - If the subject cannot be contacted or is successfully contacted but still fails to be seen for a scheduled study visit, a certified letter must be sent to the subject indicating the importance of follow-up and should be instructed to contact the site immediately. The letter should indicate that failure to reply within 30 days of the letter date will result in study discontinuation and no future study-related activities will be provided. Certified letters do not need to be sent for subsequent missed study visits if a previous delivery attempt was unsuccessful (letter returned or accepted with no subsequent response).

A subject should be considered lost to follow-up when:

- A subject in the Treatment Phase does not report for V8
- The safety follow-up contact (if applicable) is missed and three documented contacts and a certified letter do not result in subject contact within 14 days of the end of the expected contact window

7.17.5 Withdrawal of Consent

Subjects expressing a desire to withdraw consent for participation in this study should have no further study-related activities conducted. It is preferable that a subject documents her withdrawal of consent in writing.

8. DATA QUALITY CONTROL AND ASSURANCE

Electronic Case Report Forms (eCRFs) for this study will be designed and provided by [REDACTED]

[REDACTED] eCRFs will be completed by authorized study staff at each study location and transmitted to [REDACTED]. Daily diary entries by the subject will be entered into an eCRF by site staff. [REDACTED] will be responsible for data management of this trial, including quality checking of CRFs. In the event of incomplete or inconsistent data, requests for data correction will be sent to the sites for resolution. A complete audit trail of changes to the data will be maintained and available from the clinical trial database. Laboratory data (e.g., hemoglobin/hematocrit, ferritin, chemistry, quantitative hCG, urine pregnancy, Chlamydia, gonorrhea, FSH, TSH, PRL, vWF, ALT, AST) will be collected utilizing the site's local accredited laboratory (unless performing CLIA-waived tests). The site will enter the laboratory values for subjects in the clinical trial electronic database. The Data Management Plan will describe the quality checks that will be performed on the CRFs and the electronic data. CRFs and correction documentation will be converted to pdf format and bookmarked for indexing. Records retention for study data will be consistent with [REDACTED] standard procedures. Routine system backup and archiving will also be performed based on [REDACTED] standard procedures.

This study will be conducted in accordance with all applicable FDA guidances and regulations.

9. PLANNED STATISTICAL METHODS

The following statistical methods will be used to assess the efficacy and safety of LNG20 IUS for the treatment of HMB. Prior to implementing the analysis a detailed statistical analysis plan will be written.

9.1 Sample Size

Eligible subjects 18-50 years of age will include approximately 100 subjects using LNG20 IUS. The sample size estimate is based on results from previous studies with similar endpoints as well as the goal of a lower 95% confidence around the point estimate of the primary outcome with acceptable precision, i.e., being no more than 10% lower than the point estimate. The estimation of the required number of subjects needed to evaluate the efficacy of the LNG20 IUS is based on the following assumptions:

- The expected successful treatment rate is estimated to be 80% or higher
- The lower bound of 95% confidence interval should be within 10% from the point estimate, i.e., 70% or higher to establish the efficacy of LNG20 IUS for the treatment of HMB
- Early discontinuations due to dropouts, IUS expulsions, pregnancies and other reasons will not exceed 15%

A sample size of 85 will provide at least 71.5% lower bound of the 95% confidence interval for an expected successful treatment rate of 80% or higher based on normal approximation.

Therefore, 100 subjects using LNG20 IUS will provide sufficient number of subjects, for the goal of approximately 85 subjects completing the trial.

Subjects who discontinue treatment for any reason other than a one-time study IUS replacement within two weeks of a complete or partial expulsion will not be replaced.

9.2 Analysis Populations

The following subject populations will be created:

- Safety (Safety): All subjects enrolled who underwent the IUS insertion procedure, regardless of outcome.
- Modified-Intent-To-Treat (MITT): All subjects at study entry for whom the IUS is successfully placed in the uterus with valid baseline data and for whom there is at least one assessment of MBL during the treatment phase.
- Per Protocol (PP): A subset of the MITT population that excludes subjects with major protocol deviations (to be identified prior to data lock).

9.3 Disposition of Subjects

The number of subjects, who are enrolled, receive an IUS, are discontinued due to failed IUS insertion, have an IUS removal or expulsion, completed each scheduled study visit and who complete the study will be summarized.

9.4 Demographic and Other Subject Characteristics

Subject demographics and pre-treatment characteristics will be summarized.

9.5 Extent of Exposure

Exposure to study IUS will be summarized by treatment duration.

9.6 Pre-trial and Concomitant Medications

Concomitant medications include any medication or health product (any prescription medications or over-the-counter preparations) taken during the screening phase through the active study treatment phase. Pre-trial medications include any medications taken within seven days (30 days for anticoagulants) of Screening Visit 1. The number and percentage of subjects using medications, as captured on the Concomitant Medication CRF form, will be tabulated according to the medication's World Health Organization Anatomical Therapeutic Drug Class and Generic Name by treatment group and overall. Pre-trial and concomitant medications will be presented separately.

